1.0 Introduction

This document describes the planned statistical analyses to be performed for the clinical trial: "The effectiveness of radial extracorporeal shock wave therapy (rESWT), sham rESWT, standardised exercise program or usual care for patients with plantar fasciopathy". It is intended to supplement the study protocol (1).

The overall purpose of this study is to evaluate whether radial extracorporeal shock wave therapy (rESWT), sham-rESWT or a standardised high-load strength training program is more effective on change in heel pain than usual care in the treatment of plantar fasciopathy.

1.2 Research hypothesis

Null hypothesis

H₀: There is no difference between rESWT, sham-rESWT and a standardised exercise programme on change in heel pain (primary outcome) and functioning (secondary outcomes) compared to usual care in the treatment of plantar fasciopathy at 6 months follow-up (and secondary outcomes at 12 months follow-up).

Alternative hypothesis

- H₁: There is a difference between rESWT and usual care on change in heel pain (and secondary outcomes) at 6 months follow-up (and secondary outcomes at 12 months follow-up).
- H₂: There is a difference between sham-rESWT and usual care on change in heel pain (and secondary outcomes) at 6 months follow-up (and secondary outcomes at 12 months follow-up).
- H₃: There is a difference between the standardised exercise programme and usual care on change in heel pain (and secondary outcomes) at 6 months follow-up (and secondary outcomes at 12 months follow-up).

2.0 Study methods

2.1 Trial design

The study is designed as a double- blind, randomized, sham-controlled trial, with four parallel groups.

2.2 Randomization

Eligible patients were randomized in a 1:1 ratio. Treatment allocation was done by a computer generation randomization schedule with blocks of 8.

2.3 Sample size

The sample size was based on the primary outcome measure Numeric Rating Scale (NRS) at 6 months, for a comparison between two of the treatment groups using a two-sided t test. With a statistical test power of 90%, a significance level of 5 %, an assumed difference of 2 of NRS (2), estimated standard deviation (SD) of 2.7 (based on previous clinical data from the Department of Physical Medicine and Rehabilitation) and a dropout of 20%, the sample size was estimated to be 200, with 50 in each group.

2.4 Endpoints/outcome

2.4.1 Primary outcome measure

Numeric rating scale (NRS) is a patient reported pain intensity scale ranging from 0 (no pain) to 10 (worst possible pain) (3). We asked the patients to rate their pain in activity the last week, and measured change in NRS between baseline and 6 months follow-up.

2.4.2 Secondary outcome measures

Foot Function Index, revised, short form (FFI-RS) is a region specific patient reported outcome measure. FFI-RS consists of 34 questions. Scoring is from 0-100 where lower score indicate better foot health status (4). Measured after 6 and 12 months.

RAND-12 is a generic PROM measuring health related quality of life. RAND-12 has 12 items, were six create the Mental Health Composite (MHC) and the remaining the Physical Health Composite (PHC). Scoring is from 0-100, were higher score indicate better health related quality of life (5). Measured after 6 and 12 months.

Numeric rating scale (NRS) (in rest the last week). Measured after 6 and 12 months. *Numeric rating scale (NRS)* (in activity the last week). Measured after 12 months. *Patient Global Impression Of Change (PGIC) scale* is 7-point scale ranging from "very much improved" to "very much worse". The questioning is "Compared to the start of the study what is your general health status today"(6). Measured after 6 and 12 months.

| | Enrolment | Allocation | Interventions | Follow-up | Follow-up | Follow-up |
|--|-----------|------------|---------------|-----------|-----------|-----------|
| Timepoint | 0 | 0 | 0-3 months | 3 months | 6 months | 12 months |
| Assessments: | | | | | | |
| Baseline variables 1) | Х | | | | | |
| NRS 2) | Х | | | Х | Х | Х |
| FFI-RS 3) | Х | | | Х | Х | Х |
| RAND-12 4) | Х | | | Х | Х | Х |
| PGIC 5) | Х | | | Х | Х | Х |
| Other variables 6) | | | | Х | Х | Х |
| Clinical examination, ultrasound 7) | Х | | | | Х | X |

2.5 Timing of outcome assessments

1)Baseline variables: age, sex, relationship status, education, work situation, sick leave, duration of symptoms, previous treatment, previous use of radial extracorporeal shock wave treatment, use of pain medication, physical activity, smoke/non-smoker, expectation of change in foot pain, which treatment he/she hopes to get in the trial. In addition the physician register sick leave status and if the sick leave is because of foot pain. 2) NRS: Numeric Rating Scale. 3)FFI-RS: Foot Function Index revised short form. 4) RAND-12: RAND-12 Health Status Inventory.5)PGIC: Patient Global Impression of Change. 6) Other variables: Use of foot orthosis, side effects of treatment, use of other treatment modalities, use of pain medication. 7) Clinical examination includes palpation of the ankle and foot including the insertion of the

plantar fascia, weight-bearing ankle dorsiflexion motion, calf-raise test, measurement of calf circumference. In addition and only at inclusion: Measure of height, weight, body mass index, measure of passive range of motion in the ankle joint.

The ultrasound measures include thickness in millimeter, hypo echogenicity (presence/no presence), neovascularization (presence/no presence) and calcification (presence/no presence).

At baseline the patients completed the patient- reported outcome measures (PROMs): Numeric Rating Scale (NRS) (primary endpoint), RAND-12 Health status inventory (RAND-12) and Foot Function Index revised short form (FFI-RS) (secondary outcomes). In addition they completed a questionnaire including patient characteristics, anthropometric data and the duration of symptoms.

After 3 months, the patients received a letter with the same PROMs and in addition the Patients'Global Impression of Change Scalge (PGIC), which they filled out and returned. In addition they filled out a questionnaire regarding use of foot orthosis, side effects of treatment, use of other treatment modalities, and use of pain medication.

The patients were asked to complete the same PROMs and questionnaire as stated above prior to clinical examination and ultrasound at the 6- and 12 months follow-up visit.

At baseline, 6 months and 12 months follow-up the patients had a clinical examination including ultrasound.

3.0 General considerations

3.1 Adherence and protocol deviations

The number and proportion of patients that received the intervention they were randomized to will be presented. The following are pre-defined major protocol deviations regarded to affect the efficacy of the intervention:

- Compliance of interventions: For the rESWT, the patients have to complete at least 2 out of 3 sessions. For the training programme the patients must have attended at least 6 out of 8 sessions with the physiotherapist or at least have completed 30 of 36 exercise sessions.
- Timing of follow-up visits: Patients not completing post baseline follow-up within +/- 4 weeks for the 3 months follow-up, +/- 4 weeks for the 6 month follow- up, and +/- 8 weeks for the 12 month follow- up.

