3.2 Analysis populations

We define the following patient population in this trial:

- Intention- to- treat analysis set: All patients that have been randomized will be analyzed according to the group they were originally assigned, regardless what treatment (or not) they received.
- Per protocol analysis set: All patients that were randomized, received treatment according to protocol without deviations (as described for in "compliance of

interventions" and "timing of follow-up visits" above) were analyzed according to the treatment they were randomized to.

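### The per-protocol set does not exclude patients who receive another arm's treatment, so crossover stays in the per-protocol analyses of the secondary outcomes

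*SAP*

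**What the plan says.** Section 3.1 opens with a descriptive commitment: "The number and proportion of patients that received the intervention they were randomized to will be presented". It then introduces a list: "The following are pre-defined major protocol deviations regarded to affect the efficacy of the intervention". The list has two items.

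- Compliance. For shock wave treatment: "For the rESWT, the patients have to complete at least 2 out of 3 sessions". For exercise: "For the training programme the patients must have attended at least 6 out of 8 sessions with the physiotherapist", or else 30 of 36 exercise sessions completed.
- Timing. "Timing of follow-up visits: Patients not completing post baseline follow-up within +/- 4 weeks for the 3 months follow-up", with 4 weeks either side at 6 months and 8 weeks at 12 months.

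Section 3.2 defines the per-protocol set as randomised patients who "received treatment according to protocol without deviations (as described for in 'compliance of" interventions and timing of visits, analysed in the arm to which they were randomised.

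Section 2.5 lists what the questionnaires at 3, 6 and 12 months collect besides the outcome scales: "Use of foot orthosis, side effects of treatment, use of other treatment modalities, use of pain medication". No rule in the SAP uses the item on other treatment.

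Section 4.1.1 puts the primary analysis on the intention-to-treat set. Section 4.1.2 analyses the secondary outcomes on both sets. Under 2.4.2 those outcomes include FFI-RS, RAND-12, resting NRS and PGIC at 6 and 12 months, and activity NRS at 12 months.

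**The concern.** A per-protocol analysis is meant to show the contrast among patients who were treated as allocated. The list in 3.1 catches patients who had too little of their own treatment. It does not catch patients who had someone else's. Treatment ends at 3 months and follow-up runs to 12, so there is ample time for a patient still in pain to seek rESWT or exercise elsewhere. The SAP anticipates this far enough to ask about other treatment at every follow-up.

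The filter is also uneven. rESWT and exercise patients are selected for adherence, while usual-care patients can leave the set only through visit timing. Usual care is the comparator in all three alternative hypotheses, so a problem in that arm reaches every planned contrast. Retained crossover and one-sided adherence selection need not bias the result in the same direction. Agreement or disagreement between the per-protocol and intention-to-treat results would then be hard to interpret, and most so at 12 months.

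**Working it through.** **The rule, arm by arm (sections 3.1 and 3.2)**

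| Arm | Minimum attendance | Visit window | Another arm's treatment |
|---|---|---|---|
| rESWT | 2 of 3 sessions | yes | not addressed |
| Sham-rESWT | not named | yes | not addressed |
| Exercise | 6 of 8, or 30 of 36 | yes | not addressed |
| Usual care | none | yes | not addressed |

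Applied literally, a usual-care patient who has rESWT elsewhere at month 4 and attends at 6 and 12 months within the windows has no listed deviation. The same holds for a sham patient with outside rESWT.

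**The plan's own figure first (section 2.3)**

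Inputs: difference 2, SD 2.7, two-sided 5% t test, power 90%, dropout 20%. The t test needs 39.3, rounded up to 40 per group. Then 40 / (1 − 0.20) = 50 per group and 4 × 50 = 200. The stated sample size is reproduced.

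**Illustration of dilution in usual care**

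The SAP gives no crossover rate, so c below is assumed. Suppose a share c of usual-care patients obtains the compared treatment and its full effect. The difference becomes 2 × (1 − c). With 40 per arm, SE = 2.7 × √(2/40) = 0.604, on 78 degrees of freedom.

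| c | Difference, crossovers kept | Power | Usual-care n, crossovers removed | Power at difference 2.0 |
|---|---|---|---|---|
| 0% | 2.0 | 90.5% | 40 | 90.5% |
| 5% | 1.9 | 87.5% | 38 | 89.8% |
| 10% | 1.8 | 83.8% | 36 | 88.9% |
| 20% | 1.6 | 74.5% | 32 | 86.9% |
| 30% | 1.4 | 62.9% | 28 | 84.2% |

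The last two columns ignore any selection bias from removing patients.

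These are not forecasts for the per-protocol analyses. The inputs belong to activity NRS at 6 months, for which no per-protocol analysis is specified. The 40 per arm allows for dropout only, not for compliance or timing exclusions. The proportional dilution would be the same in the intention-to-treat set.

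**Direction when sham patients cross over**

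Let s be the true advantage of sham over usual care and B that of the outside treatment. If a share c of sham patients obtains it and no usual-care patient does, the sham contrast becomes s + c × (B − s). With s = 0, B = 2 and c = 20% (all assumed), it is 0 + 0.2 × 2 = 0.4. The contrast widens instead of shrinking.

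**The case against.** The strongest reply is that section 3.2 sets two conditions: treatment according to protocol, and absence of the listed deviations. The parenthesis qualifies the second, so a patient with outside rESWT might fail the first. That reading is open. But the SAP gives no way to apply the first condition, and the only working criteria are the two in the parenthesis. Two analysts could build different sets from the same sentence.

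A second reply is that the protocol, which is not shown, may define usual care broadly enough to include exercise or rESWT. If so, excluding those patients would be wrong. This stands, and the fix must allow for it. It is also fair that an arm with no scheduled sessions in the SAP has no attendance to threshold, so part of the unevenness follows from the choice of comparator.

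Third, in a sham-controlled design the 2-of-3 rule was probably meant for both shock wave arms. That is likely, but the text does not say so, and an attendance minimum would not address crossover anyway.

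Fourth, the count of patients who received their allocated treatment is to be reported. That is useful but excludes no one, and it need not capture treatment added on top of the allocation.

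Finally, removing treatment seekers has its own bias. This stands as well and is a cost of the repair.

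**Conclusion.** The point holds for the per-protocol set. As written, the operational rule keeps patients who received another arm's treatment, and the per-protocol results promised in section 4.1.2 inherit that. It is worth correcting, but it bears on a supportive analysis.

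Three stronger conclusions might be inferred, and the SAP supports none of them.

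- That the trial's main result is compromised. The primary analysis is intention-to-treat, and the per-protocol set is named only for secondary outcomes.
- That every contrast with usual care shrinks. This follows for crossover in usual care, if the outside treatment works. Crossover in sham could enlarge sham versus usual care.
- That the per-protocol analyses lose a known amount of power. With no crossover rate given, the fall from 90.5% to between 87.5% and 62.9% rests on assumed rates of 5% to 30%, full effect in those who cross over, and the primary outcome's sample-size inputs.

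The conclusion assumes that the parenthesis in 3.2 is the working definition, and that the protocol does not make the other arm's treatment part of the allocated one.

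**What to change.** In section 3.1, add a third major deviation for all four arms: receipt, outside the allocation and before the visit analysed, of another arm's study treatment (rESWT or the trial exercise programme), unless the protocol makes that treatment part of the allocated arm. Name the follow-up questionnaire item on other treatment as the source. Apply the rule by visit. If start dates are not recorded, apply it from the first visit at which the treatment is reported and at all later visits. Refer to the new item in the parenthesis in 3.2.

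State that the 2-of-3-session rule applies to both rESWT and sham-rESWT. Report crossover by arm and visit beside the intention-to-treat results. Fix all of this before group comparisons are seen.

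The cost is SAP wording and the coding of an item already collected. The SAP does not show that the type and start date of outside treatment are recorded, so the by-visit rule may have to be coarse. The per-protocol set becomes smaller and possibly more selected, because those who seek treatment are probably those still in pain. Values removed would also rest on the missing-at-random assumption in section 4.2. The per-protocol results must therefore be read beside intention-to-treat, which stays primary and unchanged. The sample size of 200 does not change.

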4.1.2 Analysis of secondary outcomes

For secondary outcomes, assessed at multiple time points (baseline, 3, 6 and 12 months) will be analysed by using a linear mixed effect model approach as described in section 4.1.1 on both the intention-to treat population and the per protocol population

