4.2 Missing data

Missing items on FFI-RS and RAND-12 will be imputed if less than 25% of the answers are missing using Predictive Mean Matching. If more than 25% of the items are missing, no score will be computed.

Missing data for repeated measured continuous endpoints will be implicitly handled by the linear mixed-effects models under the assumption of missing at random observations; thus no imputation is required.

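### The per-protocol set drops a whole patient for one late or missed visit at any time point, discarding valid 6-month data from the per-protocol analyses of secondary outcomes

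*SAP*

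**What the plan says.** SAP section 3.1 names two kinds of "pre-defined major protocol deviations regarded to affect the efficacy of the intervention". One is treatment compliance, with attendance thresholds for rESWT and for the training programme. The other is visit timing: "Patients not completing post baseline follow-up within +/- 4 weeks for the 3 months follow-up", a window of the same width at 6 months, "and +/- 8 weeks for the 12 month follow- up".

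Section 3.2 defines the per-protocol set as "All patients that were randomized, received treatment according to protocol without deviations", and refers back to both criteria.

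Section 4.1.2 analyses the secondary outcomes, measured at baseline, 3, 6 and 12 months, by mixed model "on both the intention-to treat population and the per protocol population". Section 4.1.1 places the primary analysis on the intention-to-treat population. Under section 4.2, missing repeated measurements are "implicitly handled by the linear mixed-effects models under the assumption of missing at random observations".

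**The concern.** The unit of exclusion is the patient. No sentence ties a window to the time point being analysed, and none keeps a patient while setting one late assessment aside. Four consequences follow.

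- A patient treated as allocated and seen on time at 3 and 6 months leaves every per-protocol analysis if the 12-month visit is late or missed. The 6-month value was already recorded and cannot be affected by what happens at 12 months.
- The 3-month assessment is a mailed questionnaire (section 2.5). A form returned outside its window removes the patient from the 6- and 12-month per-protocol contrasts too.
- Patients with a missed visit are excluded before the model is fitted, so the missing-at-random handling in 4.2 has little left to do in this set.
- Section 3.1 gives no compliance criterion for usual care, the reference arm of every comparison. Per-protocol membership in that arm is therefore decided by visit timing alone.

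At stake are the precision of the per-protocol estimates of secondary outcomes, and an added layer of selection on attendance that has no evident link to whether treatment was received.

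**Working it through.** **The plan's own figure.** Inputs from section 2.3: difference 2, SD 2.7, two-sided 5%, power 90%, drop-out 20%. The exact two-sample t test needs 39.3, so 40 per arm. Then 40 / (1 − 0.20) = 50 per arm and 4 × 50 = 200 in total, as stated. The sample size is not in dispute; it only supplies the starting numbers below.

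**Assumptions.** The SAP gives no rate of out-of-window visits. Let q be the proportion of remaining patients outside the window at each visit, the same at 3, 6 and 12 months. Take the 20% drop-outs as gone before 6 months, which leaves 50 × 0.80 = 40 per arm, and ignore losses from the compliance rule. Anyone lost between 6 and 12 months would be a further loss under the current rule.

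**Formulas, with lateness independent between visits.**
- Current rule, all three visits in window: 40 × (1 − q)³
- Visit-level rule, patients with an in-window 6-month value: 40 × (1 − q)
- Standard-error ratio, current to visit-level: √[(1 − q) / (1 − q)³] = 1 / (1 − q)

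| q | Current rule, per arm | Visit-level rule, per arm | In-window 6-month records discarded | SE ratio |
|---|---|---|---|---|
| 5% | 40 × 0.857 = 34.3 | 38 | 3.7 (10%) | 1.05 |
| 10% | 40 × 0.729 = 29.2 | 36 | 6.8 (19%) | 1.11 |
| 15% | 40 × 0.614 = 24.6 | 34 | 9.4 (28%) | 1.18 |

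The SE ratio compares counts of observed 6-month values only. It ignores what the mixed model would borrow from a patient's other visits.

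**Dependence between visits.**
- Same patients late every time: both rules keep 40 × (1 − q) = 38, 36 or 34 per arm. No in-window 6-month record is lost.
- Different patients late each time: the current rule keeps 40 × (1 − 3q) = 34, 28 or 22 per arm. The SE ratio is √(38/34) = 1.06, √(36/28) = 1.13 or √(34/22) = 1.24.

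**Cross-check without a separate drop-out step.** If 10% of visits are late or missed, independently, the current rule keeps 50 × 0.9³ = 36.5 per arm against 50 × 0.9 = 45. It discards 8.5, again 19% of the available 6-month records.

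**The case against.** **The harm is limited in reach.** This stands. The primary outcome is analysed by intention to treat (4.1.1), and every secondary outcome also has an intention-to-treat analysis in which the 4.2 handling works as intended. A reader might infer that the trial's main conclusion is at risk; the documents do not support that.

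**The size is unknown.** This also stands. No lateness rate is given, and clustered lateness could reduce the loss of in-window 6-month records to none. The loss could also be expressed as power: with difference 2 and SD 2.7, 10% independent lateness gives about 79% against 87%. That is for scale only. Those inputs belong to the primary NRS outcome, for which the plan names no per-protocol analysis, and section 2.3 gives no difference or SD for any secondary outcome.

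**The direction of bias is not established.** Correct. A reader might suppose that non-attenders are those who have recovered or become discouraged. Nothing in the SAP says so, and the direction of any selection bias is unknown.

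**A strict patient-level set is pre-specified and objective, and section 3.1 regards timing as affecting efficacy.** Only the first part helps the plan. The schedule in section 2.4.2 places the interventions at 0–3 months, so a late 12-month visit cannot alter treatment received or a 6-month value already recorded.

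**Other readings are possible.** The timing bullet might mean a patient who fails all three windows, or only assessments made late and not those missed. The first sits badly with a set restricted to patients without deviations. The second would keep drop-outs but would still remove a patient for one late visit. If either was meant, the text needs to say so, because two analysts could build different sets.

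**Some missingness would remain.** True: section 4.2 computes no score when more than 25% of items are missing. The handling is therefore largely bypassed rather than wholly emptied.

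**Conclusion.** The point holds as a moderate fault in an analysis-set definition. On their natural reading, sections 3.1 and 3.2 remove all of a patient's data for one out-of-window or uncompleted visit at any time point. This discards valid in-window observations from the per-protocol analyses of secondary outcomes and selects on later attendance.

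Under the stated assumptions, the 6-month contrast loses about 10% to 28% of its in-window records for lateness of 5% to 15% per visit. The loss is none if lateness is fully clustered in the same patients, and larger if it is spread over different ones. These figures illustrate scale and do not predict this trial's losses.

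A reader might also infer that the rule alone is what prevents a difference between intention-to-treat and per-protocol results from being attributed to compliance. That goes too far: excluding non-compliers is itself selection after randomisation, and the arms have different compliance criteria, with none for usual care. Such a difference would stay hard to interpret under any timing rule.

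**What to change.** In sections 3.1 and 3.2, apply the timing window to the visit and leave its width unchanged. State that, for per-protocol analyses:

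- an assessment outside its window is treated as missing for that time point only;
- a missed visit is missing for that time point and does not by itself remove the patient;
- the patient's baseline and other in-window visits stay in the mixed model, under the missing-at-random assumption already in 4.2;
- exclusion of the whole patient is reserved for treatment non-compliance as defined in 3.1.

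This takes about two sentences and no new data. The number contributing will differ by visit and must be tabulated by arm and time point. The change removes avoidable data loss and the exclusion of whole patients for attendance. It does not by itself make a difference between the intention-to-treat and per-protocol results attributable to compliance, and the report should not present it that way.
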